## FLOW CHART

Barthel Index 							X	X
Conclude subject participation 								X

1. Informed consent needs to be signed before any procedure related to the study. When it is signed, all AEs and concomitant treatment occurring after Informed Consent have to be recorded. Procedures which are performed as part of routine clinical care prior to obtaining the informed consent could be used for screening if they are within the allowed time window (after stroke onset and before drug administration). (considered by investigator).
2. Either CT or MRI is mandatory before Alteplase administration to exclude ICH (absolute contraindication) or mimic stroke (e.g. cerebral tumor) and to determine whether CT hypodensity or MRI hyperintensity of ischemia is present. The brain imaging should be interpreted by a physician with expertise in reading CT and MRI. Investigator could make decision whether or not an imaging outside the site could be used for evaluation of inclusion/exclusion criteria.
3. Cerebral image: between 22 and 36 hours after starting the infusion of trial medication.
4. Optional in case of clinical deterioration (considered by investigator)
5. For some lab results used for eligibility evaluation, e.g., random blood glucose, coagulation items, platelet, it is mandatory to get their results before drug administration. For other lab results, it is recommended but not mandatory (considered by investigator).
6. Optional in case of clinical deterioration or clinical demand (considered by investigator)
7. It is acceptable whether it is test with blood or urine (considered by investigator), but it is mandatory to have the test result verified by investigator before administration, since it might impact eligibility evaluation, too.
8. Strongly recommended, the same person should conduct all neurological questionnaires for each individual patient.
9. Trial completion:
  - At the end of visit 5 (Day 90 per protocol) for patients who have completed the trial on treatment and came to future visits as planned.
  - After early discontinuation, if a patient refuses to attend future visits as originally planned.

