## **5. VARIABLES AND THEIR ASSESSMENT**

### **5.1 TRIAL ENDPOINTS**

#### **5.1.1 Endpoints of efficacy**

##### **5.1.1.1 Primary Efficacy Endpoint**

The primary efficacy endpoint is the percentage of patients with mRS 0-1 (favourable outcome) at visit 5 (i.e., day 90) after stroke onset by face-to-face interview with patient.

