## 7.4 INTERIM ANALYSES

An interim analysis will be performed when 60 patients enter and complete the study. All the first 60 patients who complete the study will be included in this interim analysis. Both safety and efficacy will be evaluated at interim analysis.

For efficacy, a predictive probability approach in the Bayesian setting is used to help to make the decision whether the study should continue to the full enrolment and whether an early application should be submitted to CFDA upon the promising interim results.

We target  $p_s = 55\%$  as a promising response rate in the end of study. The Bayesian analysis will be performed to estimate predictive probability (PP), which is the probability that the response rate reaches  $p_s$  or above in the final study result, given the data observed at interim time-point. If the predictive probability is greater than 90%, it shows the high potential of reaching promising result in the end given interim data.

In addition, we also consider a futile response rate lower than  $p_f = 40\%$  in the end of study for early stop at the interim. We estimate the predictive probability of observing the response rate lower than  $p_f$  in the end of study given interim data. If the predictive probability is greater than 90%, it shows high potential of futility in the end. [Appendix 10.5](#) elaborates how the predictive probability is calculated.

In summary, there are 3 scenarios suggested by the interim results as below,

- Scenario A - Early submission upon promising efficacy (i.e., promising zone): PP ( $\hat{p} \geq 55\%$ )  $\geq 90\%$ , equivalently, 37 or more responders among 60 patients at interim;
- Scenario B - Early stopping upon futile efficacy (i.e., Futility zone): PP ( $\hat{p} \leq 40\%$ )  $\geq 90\%$ , equivalently, 20 or fewer responders among 60 patients at interim;
- Scenario C - Competitive zone: the rest other than promising and futility zones;

For both scenarios A and C, if there is no safety alert from independent Data Monitoring Committee (DMC), the trial will continue for the completion of recruitment of 120 patients to the end as planned to collect the sufficient safety information.

In addition to the efficacy evaluation, an independent Data Monitoring Committee (DMC) will be constituted for continuously monitoring and reviewing the safety data during the study conduction. The details of the safety monitoring scheme will be specified in DMC SAP.

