At the interim, it is envisioned that the DMC may make two types of recommendations, namely:

1. No safety issues or concerns, ethical to continue the trial as planned
2. Warning of significant safety concerns and recommendation of stopping the trial for patients' safety.

Table 7.4:1 Guidance for decision making at interim analysis

Timing and Results			Action
First 60 patients complete study			
Efficacy		Safety	
Promising Zone: $\geq 37$ patients with favourable outcome	AND	DMC declare no safety issues	Continue enrolment and early submission
Competitive Zone: $< 37$ but $> 20$ patients with favourable outcome	AND	DMC declare no safety issues	Continue enrolment without early submission
Futility Zone: $\leq 20$ patients with favourable outcome	OR	DMC declare warning of significant safety issues	early trial stopping

The guidance described in the Table 7.4.1 serves as decision base for early trial stopping or early submission to CFDA. The interim analysis in conjunction with other safety and efficacy data will be used to allow BI, in consultation with the investigators and DMC, to make a joint decision on whether the benefit and risk support continuation of the trial to the full enrolment up to 120 patients, and will help BI to make the decision on whether an early application should be submitted to CFDA.

The interim analysis will not lead to sample size recalculations and adjustment of enrolment targets.

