7. PLANNED ANALYSIS

Unless otherwise specified, the following general conventions for End-of-Text (EoT) [\[5\]](#) tables should be used regarding all descriptive statistical analysis and result presentations.

The set of summary statistics: N / Mean / SD / Min / Median / Max are for continuous data with one more decimal place compared to the original data in the subject data listing. For tables that are provided for endpoints with some extreme data, Q1 and Q3 would be preferred to Min and Max.

Tabulations of frequencies for categorical data will include all possible categories and will display the number of observations in a category as well as the percentage (%) (unless otherwise specified, all patients in the respective patient set whether they have non-missing values or not). Percentages will be rounded to one decimal place. The category missing will be displayed only if there are actually missing values. All the confidence interval calculations for proportions will use the Wilson score method.

The visit will be analysed as calculated visit and should be named ‘Baseline’, ‘Day0(1H)’, ‘Day0(2H)’, ‘Day1’, ‘Day7’, ‘Day30’ and ‘Day90’ as described in [Section 6.7](#). The units of variables should be given in the titles or column/row descriptors in square brackets (e.g. [mmHg]), unless the variable does not have a unit (e.g. scores). And the imputation rules for missing data will be applied as in [Section 6.6](#).

An independent data monitoring committee (DMC) will oversee the trial conduct, monitor safety data monthly, and review the interim analysis results when 60 patients complete the study. As for details please refer to DMC SAP. [\[6\]](#)

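### Protocol 7.4 brings the investigators into a decision based on the interim responder count, and neither document keeps that result from the people who may go on to rate mRS in an open-label, single-arm trial

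*Protocol*

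**What the plan says.** **Interim look.** Protocol 7.4 states: "An interim analysis will be performed when 60 patients enter and complete the study", and "Both safety and efficacy will be evaluated at interim analysis". Two of the three zones are set by a responder count: promising at "37 or more responders among 60 patients at interim", futile at "20 or fewer responders among 60 patients at interim". The competitive zone is everything between, 21 to 36. Table 7.4:1 pairs each zone with an action and a DMC safety statement.

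**Who decides.** The sponsor is "in consultation with the investigators and DMC, to make a joint decision" on continuing to full enrolment. The early-submission decision is described as the sponsor's own. Both DMC recommendations envisaged in Protocol 7.4 concern safety. SAP section 7 adds that the DMC will "review the interim analysis results when 60 patients complete the study". Neither document says who may or may not see the interim efficacy result. DMC details are deferred to a charter (Protocol 3.1.1) and a DMC SAP (Protocol 7.4, SAP section 7).

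**Who rates.** Protocol 5.1.1.1 has the primary endpoint assessed "by face-to-face interview with patient" and names no rater. Flow Chart footnote 8 strongly recommends that "the same person should conduct all neurological questionnaires for each individual patient". Protocol 4.1.4 declares blinding not applicable. Symptomatic intracranial haemorrhage is evaluated centrally by DMC consultants (Protocol 5.1.2.1 and 5.3.1); mRS has no such step.

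**The concern.** The efficacy claim rests on a fixed comparison: is the mRS 0-1 rate above 40%? With 120 patients that amounts to a required number of responders. Someone who knows the interim zone knows roughly how the trial stands against that number. Two routes could then move the later data. One is scoring at the boundary between mRS 1 and 2. The other is patient selection, for example through the exclusion for minor neurological deficit (Protocol 3.3.3, criterion 10), which has no numeric threshold. In a randomised trial with masked assignment, such drift would fall on both arms and largely cancel. Here nothing offsets it.

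The point is limited to what interim knowledge adds. Raters know the treatment of all 120 patients whatever is done at the interim.

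**Working it through.** **Inputs.** Null rate 40% and two-sided 0.05 (Protocol 7.2); n = 120, assumed rate 55% and power 91.5% (Protocol 7.7); interim after 60 completers (Protocol 7.4). The shift sizes and the number of patients exposed are assumptions.

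**1. The plan's own power.** Normal approximation with the null variance in the critical value:

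Power = Φ{[(0.55 − 0.40)√120 − 1.96√(0.40 × 0.60)] / √(0.55 × 0.45)} = Φ(1.373) = 91.5%.

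This matches Protocol 7.7.

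**2. The pass mark.** z = (x/120 − 0.40)/√(0.24/120). For x = 58, z = 1.86; for x = 59, z = 2.05. The test therefore rejects from 59/120. The exact probability of 59 or more responders is 2.6% at a true rate of 40% and 91.5% at 55%. The t-test named in SAP 7.4 also rejects from 59 (t = 2.00, p = 0.048). An exact test that doubles the tail gives 0.052 at 59 and so needs 60.

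**3. What the action alone reveals.** Continuing with early submission implies at least 37/60 (61.7%). Continuing without it implies 21 to 36 of 60 (35% to 60%). Continuing, with nothing else said, implies more than 20/60.

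**4. Effect of a shift after the interim.** Let m be the number of patients selected or rated after the result is known, and d the upward shift among them. With a true rate of 40%:

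P(reject) = Σᵢ P[Bin(120 − m, 0.40) = i] × P[Bin(m, 0.40 + d) ≥ 59 − i].

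| Exposed patients (m) | d = 0 | 2 points | 5 points | 10 points |
|---|---|---|---|---|
| 60 (upper bound) | 2.6% | 4.3% | 8.3% | 20.3% |
| 45 | 2.6% | 3.8% | 6.4% | 13.4% |
| 30 | 2.6% | 3.4% | 4.8% | 8.3% |
| 15 | 2.6% | 3.0% | 3.6% | 4.8% |

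Five points in 60 patients is 0.05 × 60 = 3 patients moved from mRS 2 to mRS 1. Adding the futility stop at 20/60 hardly matters (10 points, m = 60: 20.2%). With a pass mark of 60/120 and m = 60, the rate is 1.7% with no shift, 5.9% with 5 points and 15.5% with 10 points.

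**5. Why 60 is an upper bound.** The interim needs 60 patients to have completed day 90, and no pause in recruitment is stated. Patients enrolled during that wait were selected before any result existed, and some may be rated before it is known. The accrual rate is not given, so m cannot be fixed from the documents.

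**The case against.** **The rater is not named.** This stands. A reader might infer that the same investigators who join the decision also rate mRS. The documents do not say so. They only fail to separate the two groups, and the footnote asking for one rater per patient concerns continuity, not independence.

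**The exact count may not be shared, or not with every site.** This also stands. A reader might infer that each investigator will know how many more responders are needed. Protocol 7.4 does not say that counts go to all of the roughly 15 sites, and with a Coordinating Investigator in place (Protocol 3.1.1) the consultation could be narrow. Even so, it is hard to take part in a decision guided by Table 7.4:1 without learning at least the zone.

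**The DMC charter or DMC SAP may restrict access.** Possible; neither is available. A restriction there would still sit awkwardly with Protocol 7.4 as worded.

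**Raters know the treatment anyway.** True. Leniency at the 1/2 boundary is possible from the first patient, and nothing in the documents isolates the part due to interim knowledge or shows that it would be upward. That limits the size of the claim. It does not remove a separate incentive that can be avoided.

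**The DMC cannot simply replace the investigators.** Largely right. The protocol gives the DMC only safety recommendations at the interim, so it would be too strong to say that an existing efficacy role makes investigator input redundant. Hence the named sponsor group in the proposed change.

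**Conclusion.** The gap is real but modest. The protocol text brings investigators into a decision guided by the interim responder count, and no available text limits who sees that count. The primary endpoint is interview-rated, open label and uncontrolled, with no independent, central or interim-masked rater specified.

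The documents do not show that bias will occur, nor in which direction. The percentages above are illustrations that assume a true rate of 40%, rejection from 59/120 and an upward shift. A 5-point shift takes the false-positive rate from 2.6% to 4.8% with 30 patients exposed and to 8.3% with all 60. The 20.3% figure needs both a 10-point shift and full exposure, and should not be read as an expected effect.

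Nothing here calls the sample size, the 91.5% power or the interim cut-offs into question. This is a cheap improvement.

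**What to change.** In Protocol 7.4:

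- Remove the investigators from the efficacy part of the joint decision, and keep their input on safety.
- Restrict the interim efficacy counts and zone to the DMC and a small sponsor group named in advance.
- Tell sites only whether the trial continues or stops.
- Bring the DMC charter and DMC SAP into line.

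**Cost.** Wording in 7.4 and the two DMC documents, and less investigator input at the interim. Some leakage remains: continuing implies more than 20/60, and a visible early submission implies at least 37/60. The change does not mask raters to treatment.

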## **7.5 HANDLING OF MISSING DATA**

Every effort will be made to collect complete information according to the protocol. No missing values regarding vital status and intracranial bleeds are expected. However, for functional outcome parameters of surviving patients missing values might occur. The last observation carried forward (LOCF) method will be applied in the sense that data from the previous visit or measurement will substitute the missing data. In case of missing values due to death, the worst score principle will be applied.

## **7.6 RANDOMISATION**

No randomisation is required since all patients will be treated with rt-PA.

## 7.7 DETERMINATION OF SAMPLE SIZE

The study will enrol approximately 120 patients. The sample size calculation takes account into both safety and efficacy considerations.

Regarding the primary safety endpoint, an observed sICH rate of 2.4%, i.e., 3 sICH events out of 120 patients, will result in an exact binomial 95% CI (0.48%, 6.99%) with the confidence width as 6.51%, which is considered as reasonable estimation precision.

The percentage of mRS 0-1 (favourable outcome) responder at day 90 is the primary efficacy endpoint. The range of the response rate from historical review was from 40% to 60% [P05-03664]. If assuming an underlying response rate of 55% of rt-PA treatment in Chinese patients, for the planned sample size of 120 patients, a power of 91.5% can be achieved. The sample size calculations in Table 7.7.1 have been performed based on a one sample test for proportion with a two-sided significance level of 0.05 and power ranging from 80% to 90%. Calculations were performed using ADDPLAN version 6.

Table 7.7:1

Sample size calculations based on a one sample test with a two-sided significance level of 0.05 and various assumptions of percentages of mRS 0-1 responders (n=120)

Assumed mRS response rate	Number of mRS 0-1 responders	Power(%)
52.5%	63	79.4
53.3%	64	84.2
55.0%	66	91.5

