Safety criteria:	
Primary Safety endpoints:
 

The percentage of patients with symptomatic intracranial haemorrhage (sICH) within the whole study period centrally evaluated by DMC consultants, according to ECASSIII criteria, details refer to section 5.3.1.

 
Secondary Safety Endpoints:
 

Patient survival probability at visit 5 (censoring at 90 days)

		

Name of company:		Boehringer Ingelheim	
Name of finished product:		Actilyse®	
Name of active ingredient:			Alteplase (rt-PA)
Protocol date: 25 Apr 2016	Trial number: 135.331		Revision date: 15 Feb 2017
			

Frequency of death related to stroke or of neurological causes

Frequency and severity of adverse events

The percentage of patients with cerebral herniation and symptomatic edema

Statistical methods:	The sICH rate will be estimated as the proportion of patients with sICH event within the whole study period and its exact 95% confidence interval will be calculated. Efficacy endpoints will be assessed in the treated set. The proportion of mRS 0-1 (favourable outcome) responders will also be calculated along with its 95% CI. From the historical literature review, the best guess of the response rate is around 50%. It is assumed that the primary efficacy endpoint in this study will be comparable with this number. Descriptive statistics of demographic, safety and efficacy data will be presented as appropriate.		

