#### **7.3.1 Primary endpoint analyses**

The primary efficacy endpoint is the percentage of mRS 0-1 (favourable outcome) responder at day 90 after stroke onset by face-to-face interview with patient. The proportion of patients with mRS 0-1 will be presented with corresponding 95% confidence intervals (CIs).

The primary safety endpoint is the percentage of patients with symptomatic intracranial haemorrhage (sICH) centrally evaluated by DMC consultants according to ECASS III definition within the whole study period. The proportion of patients with sICH will also be presented along with corresponding 95% CIs.

Regarding the safety endpoint, the event rate of sICH observed from these studies arranged from 2.4% to 4.9% using ECASS III definition [[P05-03664](#)].

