4. CHANGES IN THE PLANNED ANALYSIS OF THE STUDY

There has been no change in the planned analyses from the statistical methods described in the CTP.

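### The sICH precision figure behind n = 120 is miscalculated, and the SAP replaces the exact interval promised for sICH with Wilson without declaring a change

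*Protocol*

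**What the plan says.** Protocol 7.7 (Determination of sample size) sets the size with "The study will enrol approximately 120 patients" and gives a safety and an efficacy justification. The safety part is one sentence: "an observed sICH rate of 2.4%, i.e., 3 sICH events out of 120 patients, will result in an exact binomial 95% CI (0.48%, 6.99" (the second limit is also a percentage), followed by a width of 6.51% that is judged reasonable.

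Three other places bear on which interval will be reported for sICH:

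- The protocol synopsis, under statistical methods, says of the sICH rate that "its exact 95% confidence interval will be calculated".
- SAP section 7 (Planned analysis) says "All the confidence interval calculations for proportions will use the Wilson score method". SAP 7.4, which covers the primary safety endpoint, makes no exception.
- SAP section 4 says "There has been no change in the planned analyses from the statistical methods described in the CTP".

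Protocol 7.3.1 promises 95% intervals without naming a method. It also gives the historical sICH rate as "2.4% to 4.9% using ECASS III definition".

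**The concern.** There are two linked faults. First, a rate of 2.4% and a count of 3 in 120 are presented as the same thing, and they are not. The printed interval has to belong to one or the other, and an exact binomial interval exists only for a whole number of events.

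Second, the protocol promises and illustrates an exact interval for the primary safety endpoint, while the SAP prescribes another method and states that nothing has changed. Both statements cannot be true.

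The null and alternative hypotheses in protocol 7.2 concern the mRS response only. For sICH the plan gives a proportion and a confidence interval, so that interval carries all of the primary safety inference, and the sentence in 7.7 is the only safety argument for 120 patients. The method should be settled before the data are seen. The trial is open label and the same SAP also governs the interim analysis of the first 60 completers, so an unresolved choice between two intervals is best closed in the text.

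**Working it through.** **Inputs.** n = 120, 3 events, stated rate 2.4%, stated limits 0.48% and 6.99%, stated width 6.51 points (protocol 7.7); historical range 2.4% to 4.9% (protocol 7.3.1); exact method (synopsis and 7.7); Wilson method (SAP section 7). All intervals are two-sided 95%.

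**Step 1: the rate.** 3/120 = 2.50%. Conversely, 2.4% × 120 = 2.88 events.

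**Step 2: reproduce the printed interval.** The Clopper-Pearson limits for x events in n are

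- lower = 0.025 quantile of Beta(x, n − x + 1)
- upper = 0.975 quantile of Beta(x + 1, n − x)

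With x = 2.88 and n = 120: lower 0.476%, upper 6.987%, width 6.511 points. These round to 0.48%, 6.99% and 6.51, so all three printed figures are recovered. The rate of 2.4% was evidently entered as a proportion with n = 120, and the result was then described as 3 events.

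**Step 3: the interval for 3 of 120.** Beta(3, 118) and Beta(4, 117) give lower 0.519%, upper 7.132%, width 6.61 points.

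**Step 4: other explanations.** For 3/120, none of Wilson (with or without continuity correction), Agresti-Coull, Jeffreys, Wald, mid-p, Blaker or the inverted two-sided binomial test gives 0.48% to 6.99%. Nor does Clopper-Pearson with 3 events and any n from 115 to 129. For example, n = 122 gives nearly the printed width (6.508) but limits of 0.510% and 7.018%.

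**Step 5: the SAP's method.** With p = 0.025, n = 120 and z = 1.96, the Wilson limits are

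[p + z²/(2n) ± z·√(p(1 − p)/n + z²/(4n²))] / (1 + z²/n) = 3.973% ± 3.120%

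that is, 0.854% to 7.093%, width 6.24 points.

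**Step 6: the other end of the historical range.** 4.9% × 120 = 5.88, so the nearest whole count is 6, and 6/120 = 5.0%. The exact interval is 1.86% to 10.57%, width 8.71 points.

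| Case | Lower | Upper | Width (points) |
|---|---|---|---|
| Printed in 7.7 | 0.48% | 6.99% | 6.51 |
| Exact, 2.88/120 (impossible count) | 0.476% | 6.987% | 6.51 |
| Exact, 3/120 | 0.52% | 7.13% | 6.61 |
| Wilson, 3/120 (SAP method) | 0.85% | 7.09% | 6.24 |
| Exact, 6/120 | 1.86% | 10.57% | 8.71 |

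**Differences.** Corrected exact against printed: upper limit 7.13 − 6.99 = 0.14 points higher; width 6.61 − 6.51 = 0.10 points greater (0.10/6.51, about 1.5%). Wilson against exact for 3/120: lower limit 0.854 − 0.519 = 0.335 points higher (ratio 0.854/0.519 = 1.65); upper limit 7.132 − 7.093 = 0.039 points lower. Exact 6/120 against the printed width: 8.71/6.51 = 1.34, about a third wider.

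**The case against.** The facts are not in dispute; their weight is. The slip in 7.7 is tiny, no stopping rule, threshold or test uses 6.99%, and the final interval will be computed from the observed count, so the error cannot reach a reported result. The sample size also rests on power for mRS. Wilson is a valid interval, it is narrower than the width 7.7 already accepts, and at the upper limit, which matters most for a harm, it differs from exact by only 0.04 points. Among statements of what will be reported, only the synopsis says exact; protocol 7.1 and 7.3.1 leave the method open, and the SAP is meant to add such detail. Showing a single precision scenario is not an error, and 6/120 lies just above the historical range.

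Much of this stands. The arithmetic slip alone is a text correction, the 6/120 line is a helpful addition rather than a repair, and the choice between exact and Wilson is not a question of validity. What does not stand is the suggestion that silence in 7.1 and 7.3.1 settles the method. The synopsis makes a specific commitment for sICH, 7.7 relies on the same method, and the SAP departs from both while stating that nothing changed.

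**Conclusion.** The concern holds on both counts.

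- **Precision statement.** The interval in 7.7 is wrong for 3 events in 120 and understates the upper limit by 0.14 points. It does not alter n = 120 or overturn the judgement of reasonable precision at this event count.
- **Method.** This is the more consequential part. As written, the SAP would report a Wilson interval for the primary safety endpoint where the protocol promises an exact one. At 3/120 this mainly moves the lower limit, from 0.52% to 0.85%.

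These figures assume that exact means Clopper-Pearson, that intervals are two-sided 95%, and that 120 patients are treated and evaluated for sICH. The correction should be made, but it does not threaten the design.

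**What to change.** 1. In protocol 7.7, restate the example as 3/120 = 2.5%, exact 95% CI 0.52% to 7.13%, width 6.61 points.
2. Preferably add a second line near the top of the historical range: 6/120 = 5.0%, exact 95% CI 1.86% to 10.57%, width 8.71 points.
3. In SAP section 7 (and 7.4), specify the Clopper-Pearson interval for the sICH proportion, as the synopsis promises. Wilson can stay for the mRS and global outcome proportions. If Wilson is preferred for sICH too, amend the synopsis and list the change in SAP section 4, so that both documents name one method.

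The cost is a text correction and one SAP sentence, with no effect on sample size, conduct or data collection. The stated precision becomes slightly less favourable.

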### **7.2 NULL AND ALTERNATIVE HYPOTHESES**

Alteplase (rt-PA) has been approved and widely used in more than 100 countries for about 20 years. Many studies were conducted by the sponsors and researchers to understand the efficacy and safety profiles of the drug for patients treated within 3-4.5 hours after AIS onset in both controlled clinical studies and real world setting. The percentage of mRS 0-1 responder at day 90 was 40.9% in SITS-ISTR [[P15-11922](#)] 52.4% in ECASS III (ITT population) and 60.9% in TIMS-China [[P13-12586](#)]. The estimation from historical review varies from 40% to 60%.

In this study, we are aiming to rule out a response rate of 40% or lower, which is considered as insufficient level of efficacy for alteplase treated within 3-4.5 hrs from stroke onset in Chinese acute ischemic stroke patients [[P13-12586](#)]. Therefore, a null hypothesis of  $p \leq 40\%$  versus an alternative hypothesis of  $p > 40\%$  will be tested using a one sample test at two-sided significance level of 0.05, where  $p$  denotes the response rate in Chinese patients who are treated within 3-4.5 hrs after stroke onset.

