7.4 PRIMARY ENDPOINT(S)

Primary analysis

The primary efficacy endpoint is the percentage of mRS 0-1 (favourable outcome) responder at Visit 5 after stroke onset by face-to-face interview with patient. The proportion of patients with mRS 0-1 will be presented with corresponding 95% confidence intervals (CIs). The imputation rules described in [Section 6.6](#) will be applied for the primary analysis. The observed case analysis, that is the proportion of patients with mRS 0-1 observed at Visit 5, will be performed as sensitivity analysis.

The null hypothesis of $p \leq 40\%$ versus the alternative hypothesis of $p > 40\%$ will be tested using a one sample t-test at two-sided significance level of 0.05. The horizontal stacked bar graphs of each level in the ordinal mRS will be presented.

The primary safety endpoint is the proportion of patients with symptomatic intracranial haemorrhage (sICH) evaluated by DMC consultants within whole study period. The proportion of patients with sICH will also be presented along with corresponding 95% CIs.

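### The stated 91.5% power holds at a 55% response rate; at the roughly 50% that the synopsis assumes for this trial, power is about 61%, and Table 7.7:1 does not show it

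*Protocol*

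**What the plan says.** The synopsis, under statistical methods, says: "From the historical literature review, the best guess of the response rate is around 50" per cent. It continues: "It is assumed that the primary efficacy endpoint in this study will be comparable with this number". It states no null value, no test and no power.

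Protocol section 7.2 sets the efficacy criterion: "we are aiming to rule out a response rate of 40% or lower". It quotes day-90 rates of 40.9% (SITS-ISTR), 52.4% (ECASS III) and 60.9% (TIMS-China) and summarises them as 40% to 60%.

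Protocol section 7.7 repeats that range and then takes a different rate: "If assuming an underlying response rate of 55% of rt-PA treatment in Chinese patients". On that condition it reports the result: "for the planned sample size of 120 patients, a power of 91.5% can be achieved". It describes the table as covering "power ranging from 80% to 90" per cent. Table 7.7:1 has three rows: 52.5% (power 79.4%), 53.3% (84.2%) and 55.0% (91.5%, in bold). There is no row at 50%.

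The figure of 55% also appears in protocol section 7.4, where it is the interim target described "as a promising response rate in the end of study". No derivation is given there either.

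SAP section 7.4 keeps the 40% null, which "will be tested using a one sample t-test at two-sided significance level of 0.05". The SAP gives no expected rate.

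**The concern.** A planning rate is the rate the trial team expects, and the power statement should say what the trial can do at that rate. Here the synopsis names one rate for this study and the power statement uses another that is 5 points higher. With a null of 40%, that changes the assumed margin from 10 points to 15.

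Someone who takes the expected rate from the synopsis and the power from section 7.7 will conclude that the trial has better than 90% power at its expected rate. Section 7.7 does not say so, but neither section corrects the impression, and the table stops above the synopsis figure. At stake is the accuracy of the stated efficacy justification for 120 patients.

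**Working it through.** **Inputs.** Null rate p0 = 0.40 and two-sided 0.05 (protocol 7.2); n = 120 and the three tabulated rates (protocol 7.7); best guess 0.50 (synopsis); one-sample t-test (SAP 7.4).

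**Step 1: reproduce the protocol's table.** The one-sample test for a proportion, with null variance at the critical value and alternative variance for the power, gives

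power = Φ( [p − 0.40 − 1.96·√(0.40·0.60/120)] / √(p(1−p)/120) ).

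The critical distance is 1.96·√0.002 = 1.96 × 0.04472 = 0.0877.

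| True rate p | p − 0.40 − 0.0877 | √(p(1−p)/120) | Ratio | Power | Table 7.7:1 |
|---|---|---|---|---|---|
| 52.5% (63/120) | 0.0373 | 0.0456 | 0.82 | 79.4% | 79.4 |
| 53.3% (64/120) | 0.0457 | 0.0455 | 1.00 | 84.2% | 84.2 |
| 55.0% (66/120) | 0.0623 | 0.0454 | 1.37 | 91.5% | 91.5 |

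All three rows match, so this is the protocol's method.

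**Step 2: apply the same formula at the synopsis rate.** At p = 0.50 the numerator is 0.10 − 0.0877 = 0.0123 and the denominator is √(0.25/120) = 0.0456. The ratio is 0.27 and the power is Φ(0.27) = **60.7%**. The chance of failing to rule out 40% is then 100 − 60.7 = 39.3%, against 100 − 91.5 = 8.5% at 55%.

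**Step 3: check with the test the SAP plans.** The t-test has a critical value of 1.980 on 119 degrees of freedom.

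- 58/120 = 0.4833: t = 0.0833/√(0.4833·0.5167/119) = 1.82, not rejected.
- 59/120 = 0.4917: t = 0.0917/√(0.4917·0.5083/119) = 2.00, rejected.

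So the trial succeeds with 59 or more responders. The binomial probability of that is **60.8%** at a true rate of 50% and 91.5% at 55%. The Wilson interval, which the SAP specifies for proportions, gives the same cut-off: its lower limit is 39.6% at 58 and 40.4% at 59.

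**Step 4: does the choice of method matter?** At 50%, other two-sided versions give 60.9% (null variance throughout), 59.7% (arcsine), 59.1% (Wald), 58.4% (noncentral-t approximation), 57.1% (continuity correction) and 53.6% (strict exact binomial, which needs 60 responders). None comes near 80%.

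**Step 5: how steep is the curve?** By the step 1 formula, power is 78.7% at the 52.4% quoted for ECASS III. It reaches 80% at a true rate of about 52.6% and 90% at about 54.6%.

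**Step 6: can 55% be recovered from the quoted rates?** The midpoint of 40% and 60% is 50%. The simple mean of the three rates is (40.9 + 52.4 + 60.9)/3 = 51.4%. Neither is 55%.

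Like the table, these figures leave out the small effect of the interim futility stop.

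**The case against.** The best case for the protocol has four parts.

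First, the 91.5% is right and is worded conditionally beside its assumption. That stands in full. Someone might infer that the power calculation is wrong; it is not.

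Second, the synopsis wording is loose. Around 50% and comparable need not mean 50.0%, and the table's first row already shows that power drops just below 80% at 52.5%. This stands as a limit on the claim: 61% is the power at exactly 50%, not across everything the phrase might cover. But the table stops above the one number the synopsis names, and the missing value lies some 19 points below the lower end of the declared power range.

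Third, 55% is plausible. Section 7.7 ties it to Chinese patients, the one Chinese figure quoted is 60.9%, and 55% is inside the 40% to 60% range and matches the interim target. So a reader who infers that the rate is unsupportable goes too far. What the documents lack is any sentence that makes this argument, and the synopsis sentence is also about this study. The interim target is a threshold for an early submission, so it does not serve as an estimate of the expected rate.

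Fourth, the synopsis reports no power, so nobody reading it alone is misled about power. That is true. The problem appears only when the two sections are read together.

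**Conclusion.** The point holds. The protocol states its power at 55% while its synopsis assumes a rate of around 50% for the same endpoint in the same trial. At 50% the power is about 61% (60.7% by the protocol's formula, 60.8% by the planned t-test), so roughly 4 in 10 such trials would fail to rule out 40%. This rests on n = 120 analysed, a null of 40%, two-sided 0.05 and a true rate of exactly 50%.

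One might go further and conclude that the trial is too small, since 80% power at 50% would take about 191 patients by the same formula. The documents do not support that step. Section 7.7 also justifies 120 by the precision of the sICH estimate, and the quoted literature leaves room for a true rate of 55% or above. Nor are the validity of the test, the confidence interval or the interim zones affected. The defect is confined to the stated efficacy justification.

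**What to change.** 1. Add a row to Table 7.7:1 for an assumed rate of 50.0% (60 responders of 120) with a power of 60.7%, and widen the power range announced in the text to cover it.
2. State in section 7.7 that power is about 61% at the synopsis best guess and 91.5% only at 55%, and give the reason for planning on 55%.
3. Reword the synopsis sentence so that it names the same planning rate as section 7.7.

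This needs text edits in two places and one table row. It adds no patients and changes no analysis or conduct. The price is that the protocol shows a less favourable power alongside the 91.5%.
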